#### **4.4. Protocol Deviations**

A protocol deviation is defined as any intentional or unintentional change to, or noncompliance with, the approved protocol procedures or requirements. Deviations may result from the action or inaction of the subject, investigator, or site staff. Significant deviations are any deviations that impact subject eligibility (i.e., protocol inclusion/exclusion violations), subject safety, subject efficacy or a subject's ability to continue in the clinical trial.

Protocol deviations will be defined and handled by CRO and reviewed by PTC. Protocol deviations will be finalized and documented prior to the database lock.

All protocol deviations will be presented in a data listing.

#### **4.5. Demographic and Baseline Characteristics**

The demographics and baseline characteristics will be summarized in the ITT population.

##### **4.5.1. Demographics**

The following demographics will be summarized by treatment arms and overall

- Age (years): as reported in the screen visit
- Gender
- Race
- Ethnicity
- Height (cm)
- Weight(kg)
- Body Mass Index (BMI) ( $\text{kg}/\text{m}^2$ ):  $\text{weight (kg)}/(\text{height in m})^2$
- BMI categories (underweight ( $<18.5$ ), normal ( $18.5 - 24.9$ ), overweight ( $25.0 - 29.9$ ), obesity ( $\geq 30$ ))
- Smoking history (smoker, non-smoker, former smoker)
- Years of smoking (years)
- Average packs smoked per week

##### **4.5.2. Baseline Characteristics**

The following baseline characteristics will be summarized by treatment arms and overall.

Stratification factors:

- Age ( $\leq 62$  vs  $>62$ )
- Dexamethasone use (yes vs no)
- Remdesivir use (yes vs no)

Baseline disease risk factors:

- Chronic kidney disease (yes vs no)
- COPD/asthma (yes vs no)
- Immunocompromised (yes vs no)
- Type 2 diabetes (yes vs no)
- Heart disease (yes vs no)
- Sickle cell disease (yes vs no)
- Obesity (yes vs no)
- Hypertension (yes vs no)

Baseline disease characteristics:

- WHO ordinal scale for clinical improvement
- Received any of COVID-19 treatment as SOC (yes vs no)
- Time from symptom onset to randomization
- Time from COVID-19 diagnosis to randomization
- COVID-19 initial symptoms

#### **4.6. Medical History**

All medical history will be coded using Medical Dictionary for Regulatory Activities (MedDRA). The MedDRA version will be indicated in the footnote of the relevant tables and listings based on the version used in the clinical data. A summary of medical and surgical history will be presented by MedDRA system and organ class and preferred term (PT).

Medical history will be presented in by-subject listings as well.

#### **4.7. Prior/Concomitant/Post Medications/Procedures**

Prior medications/procedures are defined as non-study medications/procedures that were initiated prior to the start of study treatment. Concomitant medications/procedures are defined as non-study medications/procedures that were initiated before the first dose of study drug and continued during the study treatment or initiated on/after the first dose date but before the end of study treatment. Post medication/procedures are defined as non-study medications/procedures that were initiated after the last dose of study treatment up to Day 28 or medications/procedures initiated prior to the last study treatment and continued after the last dose. It is possible that some medications/procedures can be counted in more than 1 category. A medication/procedure flag will be created for each medication/procedure to indicate the type of the medication/procedure (ie, prior or concomitant or post). Medications with missing start or end dates will be categorized as either prior or concomitant or post or all unless there is evidence contradictory. For example, if the start date of a medication/procedure is missing and the end date is prior to the first study treatment date, the medication/procedure will be considered as prior. If the end date is after the first study treatment date or is missing or the medication/procedure is ongoing, the medication/procedure will be considered concomitant or post.

All non-study drugs and therapies will be coded by Anatomical Therapeutic Chemical (ATC) code and PT using the World Health Organization Drug Dictionary (WHODD). All procedures will be coded by the MedDRA. The WHODD and MedDRA versions will be indicated in the footnote of the relevant tables and listings based on the versions used in the clinical data.

#### **4.7.1. COVID-19 Standard of Care Medications**

All prior/concomitant COVID-19 standard of care medications will be categorized as:

- COVID-19 medications initiated and ended prior to the first study treatment
- COVID-19 medications initiated prior to the first study treatment and continued during the study
- COVID-19 medications initiated after the first study treatment as part of SOC but not as rescue medications
- COVID-19 medications initiated after the first study treatment as rescue medications

COVID-19 standard of care medications will be summarized with subject counts and percentages by the above medication categories, WHO ATC level 3, and PT and by treatment groups.

#### **4.7.2. COVID-19 Procedures**

Number and percent of the subjects who undergo COVID-19 procedures (i.e., CT scan, x-ray, and other) as well as the results (normal and abnormal) will be summarized by study visit, and treatment groups. Subjects requires mechanical ventilation during the study will be summarized by treatment groups.

#### **4.7.3. Other Prior/Concomitant/Post Medications**

Prior medications other than medications used for COVID-19 will be summarized with subject counts and percentages by WHO ATC level 3 and PT and by treatment groups and overall.

Concomitant medications other than medications used for COVID-19 will be summarized with subject counts and percentages by WHO ATC level 3 and PT and by treatment groups and overall.

Post medications other than medications used for COVID-19 will be summarized with subject counts and percentages by WHO ATC level 3 and PT and by treatment groups and overall.

All prior concomitant and post medications/procedures including medications/procedures used for COVID-19 will be listed.

#### **4.8. Study Drug Exposure**

Treatment duration, and treatment compliance will be summarized by treatment groups and overall.

##### **4.8.1. Treatment Duration**

Treatment duration (days) is defined as the date of last study dose - the date of first study dose +1. For subjects who are still on treatment at a data cut-off (extraction) date, the last dose date is the last dosing date on or prior to the data cut-off date.

#### 4.8.2. Treatment Compliance

Treatment compliance is defined as  $[\text{total cumulative dose received}/\text{total cumulative dose prescribed}] \times 100\%$ , where the total cumulative dose received is defined as the sum of all doses taken in mg during the treatment period and the total cumulative dose prescribed is defined as the sum of all doses prescribed. For example, if a subject completed 14 days of treatment, the total cumulative dose prescribed is calculated as  $200 \text{ (mg)} \times 2 \text{ (BID)} \times \text{first 7 (days)} + 50 \text{ (mg)} \times 1 \text{ (QD)} \times \text{second 7 (days)} = 3150 \text{ (mg)}$

Study drug exposure will also be presented in by-subject listings.

#### 4.9. Efficacy Analysis

Efficacy analyses will be based on the ITT population. The null hypothesis for primary efficacy comparison is that the distribution of time to respiratory improvement (T2RI) between the two treatment groups is the same. The alternative hypothesis is that the distribution of T2RI between the two treatment groups is not the same. Rejecting the null hypothesis with shortened T2RI in PTC299 as compared with the placebo arm in the ITT population will be considered a successful demonstration of efficacy.

All statistical tests will be 2-sided at the significance level of 0.05. The corresponding p-values and 2-sided 95% CIs for intended point estimates will be reported.

##### 4.9.1. Primary Efficacy Analysis

The primary endpoint is the time from randomization to respiratory improvement (T2RI), defined as  $\text{SpO}_2 \geq 94\%$  on room air sustained until discharge from the hospital or the end of the study (Day 28).

All hospitalized subjects will be followed fully to Day 28 with efficacy measurements taken daily unless they die, are lost to follow-up, or withdraw consent. For subjects who are discharged from the hospital prior to Day 28 without achieving respiratory improvement,  $\text{SpO}_2$  measurements will be taken daily until Day 28. All measurements recorded will be used for efficacy analysis.

Subjects who achieved  $\text{SpO}_2 \geq 94\%$  and sustained to Day 28 or discharge without taking any COVID-19 rescue therapy during the study will be considered as achieving respiratory improvement event and the event date will be the first date of achieving  $\text{SpO}_2 \geq 94\%$ . For all other subjects i.e., a). randomized but had no follow-up; b). initiated any COVID-19 rescue therapy during the study, where a rescue therapy is defined as any additional medication, exclusive of SOC, used to treat worsening of COVID-19 symptoms and recorded as rescue therapy on the eCRF; c). lost follow-up prior to Day 28 d). died prior to Day 28; e). withdrawn consent prior to Day 28; f). had full follow-up without achieving sustained  $\text{SpO}_2 \geq 94\%$ , will be censored at Day 28.

Kaplan-Meier (KM) plots of time to respiratory improvement will be presented. Median time to respiratory improvement will be estimated via the Kaplan-Meier product limit method.

A two-sided 95% confidence interval (CI) for the median time to respiratory improvement will be computed for PTC299 and placebo cohorts based on a log-log transformed CI for the survivor function  $S(t)$ . Time to respiratory improvement will be compared between treatment groups using stratified log-rank test by randomization strata.

Hazard ratio and corresponding two-sided 95% CIs will be estimated using a Cox proportional hazards model, with treatment arm as a single covariate, stratified by the stratification factors.

Respiratory improvement rates at Days 7, 14, and 28 will also be estimated using KM estimates on the time to respiratory improvement curve. Associated two-sided 95% CIs for each treatment group and the difference between the 2 treatment groups will be calculated using Greenwood's formula for variance derivation.

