5.5. Concomitant Therapy

All subjects in both cohorts will receive SOC, according to written local guidelines and practices.

Concomitant use of steroids (except dexamethasone), sensitive CYP2D6 substrates, CYP2C inducers, IL-6 neutralizing antibodies, IL-6 receptor inhibitors, or any investigational therapy will not be permitted.

Caution should be used in the concomitant administration of breast cancer resistance protein (BCRP) substrate drugs as intestinal BCRP inhibition by PTC299 following a 200 mg BID dose of PTC299 cannot be excluded; guidance should be sought from the study Medical Monitor in each case.

An attempt will be made to record all medications taken by subjects 30 days prior to the first dose of study drug and through Day 28.

All concomitant medications (prescription and over the counter), vitamin and mineral supplements, and herbs taken during the study will be documented on the concomitant medication electronic case report form (eCRF). Information recorded will include start and stop dates, dose and route of administration, and indication.

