8.4.2. Analysis of Primary Efficacy Endpoints

The primary endpoint is time from randomization to respiratory improvement, defined as SpO₂ \geq 94% on room air sustained until discharge from the hospital or the end of the study (Day 28).

All hospitalized subjects will be followed fully to Day 28 with efficacy measurements taken daily unless they die, are lost to follow-up, or withdraw consent. For subjects who are discharged from the hospital prior to Day 28 without achieving respiratory improvement, SpO₂ measurements will be taken daily until Day 28. All measurements recorded will be used for efficacy analysis.

Subjects who achieved $SpO_2 \ge 94\%$ on room air and sustained this to Day 28 or discharge without taking any COVID-19 rescue therapy during the study will be considered as achieving the respiratory improvement event and the event date will be the first date of achieving $SpO_2 \ge 94\%$. Subjects will be censored at Day 28 if any of the following apply:

- randomized but had no follow-up
- took any COVID-19 rescue therapy during the study
- lost to follow-up prior to Day 28
- died prior to Day 28
- withdrew consent prior to Day 28
- had full follow-up without achieving sustained SpO₂ >94%.

Rescue therapy is defined as any additional medication, exclusive of SOC, used to treat a worsening of COVID-19 symptoms and recorded as rescue therapy on the eCRF.

Kaplan-Meier plots of time to respiratory improvement will be presented. Median time to respiratory improvement will be estimated via the Kaplan-Meier product limit method. A two-sided 95% confidence interval (CI) for the median time to respiratory improvement will be computed for PTC299 and placebo cohorts based on a log-log transformed CI for the survivor function S(t). Time to respiratory improvement will be compared between treatment groups using stratified log-rank test.

Hazard ratio and corresponding two-sided 95% CIs will be estimated using a Cox proportional hazards model, with treatment arm as a single covariate, stratified by the stratification factors.

Respiratory improvement rates at Days 7, 14, and 28 will also be estimated using Kaplan-Meier estimates on the time to respiratory improvement curve. Associated two-sided 95% CIs for each treatment group and the difference between the 2 treatment groups will be calculated using Greenwood's formula for variance derivation.

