### 3.7. Interim Analyses

Two interim analyses are planned. The first interim analysis will be conducted when 40 randomized subjects (approximately 20 in treatment arm and 20 in placebo arm) have received 14 days of treatment and completed 14 days of follow-up or discontinued due to death, withdrew consent, or were lost-to-follow-up. No formal statistical testing will be performed at the first interim analysis. An independent data safety monitoring board will review the safety data. Enrollment will continue if there are no safety concerns.

The second interim analysis will be conducted for futility. It will be performed when 50% of respiratory improvement events have been reached, ie, 163 events have been observed (approximately 190 subjects). Respiratory improvement is defined as  $SpO_2 \geq 94\%$  in room air until discharge from the hospital or the end of study (Day 28). All subjects who have completed through Day 28, were discharged with  $SpO_2 \geq 94\%$  on room air, withdrew consent, died, were lost to follow-up, or took any COVID-19 rescue therapy during the study will be included in the interim analysis. Subjects whose primary event cannot be determined at the interim cut, i.e., ongoing subjects, will not be included in the interim efficacy analysis. Subjects who died, withdrew consent, were lost to follow-up, or took any COVID-19 rescue therapy will be censored at Day 28. The detailed censoring rules for the primary endpoint are described in Section 4.9.1.

A stratified log-rank test will be performed, and the hazard ratio (treatment vs placebo) will be compared with the futility boundary. The trial may be stopped for futility if the hazard ratio is less than 1.091. The futility boundary is based on Lan-DeMets beta spending function (non-binding option) with overall beta of 80%.

The unblinded interim analyses will be conducted by an independent statistician and the results will be only shared with the closed session of the DSMB. DSMB will make the go- or no-go recommendation and only the recommendation will be communicated to the study team. The study team will be kept blinded for results related to the interim analyses.

For the first and second interim analyses, all safety analyses will be based on safety population and all efficacy analyses will be based on ITT population.

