#### **4.9.1.1. Sensitivity Analysis for Primary Endpoint**

Three sensitivity analyses will be performed for the primary endpoint as follows:

- Randomized subjects without any follow-up will be censored at the randomization date.
- Subjects will not be censored by rescue therapy in the primary analysis.
- An additional variable of time from symptom onset to randomization ( $\leq 7$  days versus  $>7$  days) will be added in the primary analysis model.

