#### **4.10.2. Death**

The number and the percentage of deaths at Day 28 and Day 60, respectively, will be summarized by treatment groups.

All deaths will be presented in a by-subject listing.

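### The protocol and SAP contradict each other on whether a patient who dies before Day 28, after discharge at a qualifying SpO2, counts as improved, and no sensitivity analysis varies this

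*SAP*

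**What the plan says.** **SAP 4.9.1, event.** Subjects who reach the SpO2 threshold "sustained to Day 28 or discharge without taking any COVID-19 rescue therapy during the study will be considered as achieving respiratory improvement event". The event date is the first day at the threshold.

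**SAP 4.9.1, censoring.** The list opens "For all other subjects i.e., a). randomized but had no follow-up" and goes on to include "d). died prior to Day 28; e). withdrawn consent prior to Day 28". All listed subjects are censored at Day 28.

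**Protocol 8.4.2.** The event sentence is essentially the same. The censoring list is introduced differently: a subject is censored at Day 28 when any one item applies. The items include "died prior to Day 28", loss to follow-up, withdrawal of consent and rescue, and none is limited to subjects without an event.

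**SAP 3.7 and Protocol 8.4.6 (futility interim).** Undetermined subjects are left out: "Subjects whose primary event cannot be determined at the interim cut, i.e., ongoing subjects, will not be included in the interim efficacy analysis". Death, withdrawal, loss to follow-up and rescue all lead to censoring at Day 28. SAP 3.7 then refers to SAP 4.9.1 for the detailed rules.

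**SAP 5** declares no change from the protocol's planned analyses.

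**SAP 4.9.1.1** has three sensitivity analyses. They cover subjects without follow-up, rescue ("Subjects will not be censored by rescue therapy in the primary analysis") and time since symptom onset.

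**SAP 4.10.2.** "The number and the percentage of deaths at Day 28 and Day 60, respectively, will be summarized by treatment groups". Deaths are also listed by subject.

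**The concern.** Take two patients, both discharged on Day 5 at SpO2 of at least 94% on room air. Patient A takes rescue therapy on Day 12 and is alive at Day 28. Patient B dies on Day 12 with no rescue recorded.

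The rescue condition runs for the whole study. Under Protocol 5.5 the sites try to "record all medications taken by subjects 30 days prior to the first dose of study drug and through Day 28", so rescue after discharge can be captured and A loses the event. On the literal SAP 4.9.1 rule, B keeps an improvement dated Day 5, so the worse outcome gets the better score. On the protocol list and the plain text of SAP 3.7, B is censored at Day 28 like A.

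Whoever programs the primary endpoint has to choose between these rules. The same patient could be censored at the futility interim and counted as improved at the final analysis. If the event-keeping rule is used, an excess of such deaths on one arm leaves the primary hazard ratio unchanged.

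**Working it through.** **1. The texts applied to Patient B** (qualifying discharge, no rescue, death before Day 28)

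| Text | Result for B |
|---|---|
| SAP 4.9.1, read literally | Event: the event sentence is met, so B is not among the remaining subjects |
| Protocol 8.4.2, event sentence | Event |
| Protocol 8.4.2, censoring list | Censored at Day 28 |
| SAP 3.7 and Protocol 8.4.6 | Censored at Day 28 |
| SAP 5 | SAP and protocol should agree |

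Protocol 8.4.2 meets itself here: B satisfies both its event sentence and its censoring list, and no order of precedence is given.

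**2. Sensitivity analyses.** The second one removes rescue censoring, which makes A an event and so tests the rescue half of the asymmetry. None of the three changes B.

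**3. The plan's own figures** (SAP 3.6: medians 11 and 8 days, 28 days of follow-up, 326 events, hazard ratio 1.38, two-sided 0.05; about 190 per arm)

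- Day 28 rates, exponential: 1 − 2^(−28/11) = 0.829 and 1 − 2^(−28/8) = 0.912, as stated.
- Expected events: 190 × (0.8287 + 0.9116) = 330.7, close to 326.
- Power (Schoenfeld): Z = ln(1.38) × √(326/4) = 0.322 × 9.03 = 2.91; Φ(2.91 − 1.96) = 0.828. The claim of more than 80% reproduces.

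**4. Size of the difference between the two rules.** The documents give no rate of death after discharge. The 1% to 5% in Protocol 1 is overall COVID-19 fatality and cannot be used for this. The counts below are assumptions.

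Method: 10,000 simulated trials, exponential times, 190 per arm, unstratified log-rank and Cox. A fixed number of recoveries before Day 21 is recoded from event to censored at Day 28. Success means Z > 1.96 in favour of PTC299. Repeated runs agree to about 0.01.

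| Deaths after qualifying discharge (placebo, PTC299) | HR if censored | Power if censored |
|---|---|---|
| 0, 0 | 1.38 | 0.83 |
| 1, 1 | 1.37 | 0.82 |
| 3, 3 | 1.36 to 1.37 | 0.80 |
| 5, 5 | 1.36 | 0.79 |
| 0, 1 | 1.35 | 0.78 to 0.79 |
| 0, 3 | 1.31 | 0.69 |
| 0, 5 | 1.27 | 0.56 to 0.57 |
| 3, 0 | 1.43 to 1.44 | 0.90 to 0.91 |

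Under the rule that keeps the event, every row equals the first. Of trials significant for PTC299 under that rule, about 5%, 16 to 17% and 30 to 31% lose significance with 1, 3 and 5 excess PTC299 deaths.

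The equal-count rows hold the counts exactly balanced. In a separate simulation (3,000 trials, daily times), each improver had the same risk in both arms and counts varied by chance. A risk of 1% (about 3 deaths in total) took power from 0.829 to 0.805; 3% (about 10 in total) took it to 0.761.

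**The case against.** The strongest case against has four parts.

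- **The endpoint ends at discharge, so later death lies outside it.** This is a fair reading of the endpoint sentence. But the rescue condition already looks past discharge, and the protocol list and SAP 3.7 name death without that limit.
- **Deaths are not hidden.** Day 28 mortality is a separate secondary endpoint, and deaths are tabulated by arm and listed by subject. This stands. What is missing is the link: the table does not show how many deaths were scored as improvements.
- **The affected group is narrow and may be empty.** This also stands. With equal counts little changes, and the large effects need several such deaths on one arm and none on the other.
- **SAP 4.9.1 may not mean what its literal reading says.** Its list follows an i.e., which can be taken as naming who the remaining subjects are. On that reading B is censored. This supports the finding that the rule is unsettled.

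A reader might infer that the plan has definitely chosen to count these deaths as successes. The documents do not support that, because Protocol 8.4.2, SAP 3.7 and SAP 5 point the other way. Nor is the rescue–death asymmetry wholly untested, since the second sensitivity analysis covers the rescue half.

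**Conclusion.** The point holds as an unreconciled contradiction. One type of patient is an improvement under the literal SAP 4.9.1, censored under SAP 3.7, and both under Protocol 8.4.2. No planned analysis shows what the choice does to the primary result.

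The size rests entirely on assumed counts. Equal counts of 3 to 5 per arm cost about 0.03 to 0.04 of power. An excess of 1, 3 or 5 on PTC299 would lower the hazard ratio from 1.38 to about 1.35, 1.31 or 1.27. An excess of 3 on placebo would raise it to about 1.44, so the event-keeping rule could also hide a benefit.

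A reader might also infer that the futility decision at 1.091 is distorted. That would follow only if SAP 3.7 kept these deaths as events, and its plain text censors them. The matter should be fixed, because the repair is cheap and the choice should be on record before unblinding.

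**What to change.** Before database lock:

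1. State one rule for death between a qualifying discharge and Day 28, in identical words in SAP 4.9.1, SAP 3.7 and Protocol 8.4.2 and 8.4.6. Censoring at Day 28, as for rescue, matches the protocol list and SAP 3.7.
2. In the same edit, state whether loss to follow-up or withdrawal after a qualifying discharge removes the event. The protocol list treats both exactly as it treats death, so it cannot be cited as settling death while being set aside for the other two. If the chosen SAP rule departs from the list, record it in SAP 5 or amend the protocol.
3. Add the other rule for death to SAP 4.9.1.1 as a sensitivity analysis.
4. Report by arm the numbers of deaths and of rescue uses between a qualifying discharge and Day 28.

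The cost is a SAP revision with matching protocol wording, one extra analysis and one table. No new data are needed: deaths, medications through Day 28 and length of hospital stay are already collected. If censoring is chosen, power falls slightly when such deaths are equal in both arms (about 0.83 to 0.80 at 3 per arm).

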**Time from randomization to respiratory rate  $\leq 24$  breaths/minute on room air**

Respiratory rate  $\leq 24$  breaths/minute on room air and sustained until discharge or Day 28 will be considered as achieving the respiratory rate normalization event. Time from randomization to the first date of achieving normalization of respiratory rate will be analyzed using KM method by treatment groups. A summary table of the number of events, the number of censors, and KM estimates (25th, 50th, 75th percentile of time to normalization of respiratory rate along with the 95% CI), and the rate of normalization of respiratory rate at Day 7, Day 14, and Day 28 will be provided.

Hazard ratio and corresponding two-sided 95% CIs will be estimated using a Cox proportional hazards model, with treatment arm as a single covariate, stratified by the stratification factors.

A KM plot by treatment groups will be provided for time from randomization to respiratory rate normalization and a by-subject listing will also be provided.

**Time from randomization to cough reported as mild or absent (on a scale of severe, moderate, mild, absent, in those with cough at enrollment rated as severe or moderate)**

Time from randomization to cough relief will only be analyzed in subjects with cough self-reported as severe or moderate at baseline on a scale of severe, moderate, mild, or absent. Cough relief event is defined as subjects with cough self-reported as severe or moderate at baseline and reported as mild or absent during the study and sustained until discharge or Day 28. Time from randomization to the first date of achieving cough relief event will be analyzed using KM method by treatment groups. A summary table of the number of events, the number of censors, and KM estimates (25th, 50th, 75th percentile of time to cough relief along with the 95% CI), and the cough relief rate at Day 7, Day 14, and Day 28 will be provided.

Hazard ratio and corresponding two-sided 95% CIs will be estimated using a Cox proportional hazards model, with treatment arm as a single covariate, stratified by the stratification factors.

A KM plot by treatment groups will be provided for time from randomization to cough relief and a by-subject listing will also be provided.

**Time from randomization to dyspnea reported as mild or absent (on a scale of severe, moderate, mild, absent, in those with dyspnea at enrollment rated as severe or moderate)**

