**5. CHANGES TO THE PLANNED STATISTICAL ANALYSIS IN THE PROTOCOL**

There is no change relative to the planned statistical analyses in the protocol amendment.

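### SAP 4.9.1's rule for the primary event omits room air, and the date clause in both documents does not name the start of the sustained room-air period, so the derivation conflicts with the endpoint definition

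*SAP*

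**What the plan says.** SAP 4.9.1 opens by defining the primary endpoint as time from randomization to SpO2 ≥94% "on room air sustained until discharge from the hospital or the end of the study (Day 28"). SAP 2.2.1 and protocol 2.2.1 agree.

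Two paragraphs later SAP 4.9.1 gives the rule from which a programmer would work. The condition is that the subject reached the 94% threshold "and sustained to Day 28 or discharge without taking any COVID-19 rescue therapy during the study". The consequence is that such a subject "will be considered as achieving respiratory improvement event and the event date will be the first date of achieving" that threshold. All others are censored at Day 28. The last censoring category, f), is subjects who "had full follow-up without achieving sustained" SpO2 ≥94%. Neither the event sentence nor category f) mentions room air.

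The matching sentence in protocol 8.4.2 requires SpO2 ≥94% "on room air and sustained this to Day 28 or discharge without taking any COVID-19 rescue therapy during the study". The consequence is worded as in the SAP: these subjects "will be considered as achieving the respiratory improvement event and the event date will be the first date of achieving" the threshold. The protocol therefore has room air in the event condition, but not in the date clause or in its last censoring item.

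SAP section 5 states: "There is no change relative to the planned statistical analyses in the protocol amendment".

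**The concern.** A primary-endpoint derivation must fix two things for each subject: whether the event occurred, and on which day. The operative text departs from the definition on both.

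- **Event status (SAP only).** Without the room-air condition, a subject whose saturation was held at ≥94% only on supplemental oxygen meets the event sentence and escapes category f).
- **Event date (both documents).** The date clause names the threshold, not the first day of the room-air period that lasted. An earlier reading that was transient, or taken on oxygen, could set the date.

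Such readings are foreseeable. Every subject enters with room-air SpO2 below 94% (inclusion criterion 6). One secondary endpoint is restricted to subjects not needing oxygen at baseline, which implies that others do need it. Protocol 7.2 has SpO2 monitored repeatedly through each hospital day. The Table 3 note on daily saturation for the primary endpoint does not mention room air.

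Event status and date feed the final log-rank test, the Cox hazard ratio, the medians and the Day 7, 14 and 28 rates. The date also feeds the futility comparison with a hazard ratio of 1.091. None of the three sensitivity analyses in SAP 4.9.1.1 examines dating or oxygen status.

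**Working it through.** **1. The texts side by side**

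| Element | SAP 4.9.1 | Protocol 8.4.2 |
|---|---|---|
| Opening definition | room air, sustained | room air, sustained |
| Event sentence | sustained; no room air | room air, sustained |
| Date clause | first SpO2 ≥94% | first SpO2 ≥94% |
| Last censoring item | sustained; no room air | sustained; no room air |

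The SAP is tighter for some secondary endpoints. Its respiratory-rate rule keeps the condition: "breaths/minute on room air and sustained until discharge or Day 28 will be considered as achieving the respiratory rate normalization event". Cough and dyspnea are dated at the first day of a relief event that is itself defined as sustained.

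**2. A worked subject.** SpO2 is 95% on Day 2, below 94% on Days 3 to 8, then ≥94% on room air from Day 9 to discharge. By the definition the event is on Day 9; by the literal date clause it is on Day 2, which is 9 − 2 = 7 days earlier.

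**3. The plan's own figures reproduce.** Inputs (SAP 3.6, protocol 8.2): medians 11 and 8 days, hazard ratio 1.38, 326 events, two-sided 0.05, about 380 subjects randomized 1:1.

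- Day 28 rates under exponential times: 1 − 2^(−28/11) = 0.829 and 1 − 2^(−28/8) = 0.912, as stated.
- Expected events: 190 × (0.8287 + 0.9116) = 330.7.
- Schoenfeld power: Φ(√(326/4) × ln 1.38 − 1.96) = Φ(0.948) = 82.8%, consistent with more than 80%.

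**4. What literal dating would do (illustration only).** The documents give no misdating rate, so these rates are assumed and equal in both arms. Set-up: 6,000 simulated trials per setting, 190 per arm, exponential times rounded up to whole days, unstratified log-rank test, Cox model with Efron ties. The interim has 95 per arm, about 165 events. Simulation error is about ±1.0 point for power and ±0.7 for the interim.

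| Assumed misdating | Power | Placebo median, days | Interim HR <1.091 |
|---|---|---|---|
| None | 83% | 11.5 | 6.9% |
| 1–3 days early in 10/25/50% of responders | 82/82/83% | 11.3/11.0/10.5 | – |
| Random earlier day in 10/25/50% | 82/79/78% | 10.7/9.6/7.8 | 7.2/7.8/8.1% |
| Moved to Day 1 in 10/25/50% | 79/77/72% | – | 8.0/9.7/12.7% |
| Daily chance of an early reading 5/10/20% (33/50/68% misdated) | 75/69/65% | – | 9.8/11.5/14.1% |

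In the random-earlier-day rows the mean hazard ratio goes from 1.38 to 1.37, 1.36 and 1.35. A second simulation (1,500 runs, early date uniform up to the true date) gives placebo/PTC299 medians of 11.5/8.6 days with no misdating, 9.9/7.2 at 25% and 8.2/5.9 at 50%, so both arms shift. With equal medians, two-sided rejection stays between 4.4% and 5.7% in every setting tested.

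**5. What the event-status wording could do (illustration only).** Under the design, 1 − 0.829 = 17.1% of placebo and 1 − 0.912 = 8.8% of PTC299 subjects have not improved by Day 28. If 5, 10 or 25% of them were counted as events, power would be 81, 80 or 75% with dates spread over Days 1–28, or 82, 81 or 79% with dates on Days 15–28 (hazard ratio 1.33 to 1.37). This pool is too large: deaths, withdrawals, losses and rescue users are in it, and they are censored whatever the oxygen wording. Only fully followed, unrescued subjects sustained on oxygen could be miscounted, and the documents do not give their number.

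**The case against.** The strongest reply is that the intent is plain and the operative sentence is shorthand. The definition with room air stands at the top of the same section. SAP 6.2 describes an outcome date as the first date of achieving the endpoint, which ties the date to the full definition. If section 5 is right that nothing changed, the protocol's room-air wording supplies the missing phrase. The remark that all recorded measurements are used closes a paragraph about daily measurements, and the schedule names a daily saturation for the primary endpoint. Vital signs are listed (SAP 4.10.5), so dates can be checked by hand.

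Most of this stands, and it rules out two stronger readings. A reader might infer that the SAP deliberately changed the endpoint or mandates misdating; the definition and SAP 6.2 do not support that. A reader might also infer that event status at the futility interim is affected. It is not: SAP 3.7 and protocol 8.4.6 both state room air in their own definition of respiratory improvement. Neither gives its own date rule, however, so interim dating does inherit the loose clause.

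The reply does not remove the conflict. SAP 6.2 is a general convention and does not say where a sustained period begins. The specific sentence in 4.9.1 does name a date, and followed as written it can give the wrong one.

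**Conclusion.** The point holds as a drafting conflict in the primary derivation that should be fixed. That the SAP omits room air from its event sentence and category f), that the protocol omits it from its last censoring item, and that neither date clause refers to the sustained room-air period, are matters of text and certain.

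The consequences are conditional. The likely effect of literal dating is shorter medians in both arms. There is little or no power loss if dates are 1 to 3 days early. The loss becomes material only if many events collapse to Day 1 or early readings are common. These results assume equal misdating in both arms, exponential times and an unstratified test, whereas the plan stratifies.

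It would be wrong to conclude that the trial is underpowered or that type I error is inflated. The design figures reproduce, 326 events and about 380 subjects stand, and simulated rejection under no effect stays near 5%.

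**What to change.** - **SAP 4.9.1:** restore *on room air* in the event sentence and in censoring category f).
- **Protocol 8.4.2:** add *on room air* to the last censoring item.
- **Both:** date the event at the first day of the room-air SpO2 ≥94% period that is sustained to discharge or Day 28, using the daily SpO2 that the schedule of events names for primary endpoint assessment.
- **Futility interim (SAP 3.7, protocol 8.4.6):** state that the same dating applies.

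The cost is a few words in each document, plus confirming that oxygen status is recorded with each primary-endpoint SpO2; the documents do not show whether the eCRF captures it. Sample size, event target and test do not change.
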